6.2.3.3 P-gp inhibitors

It is possible that co-administration of P-gp inhibitors (*e.g.*, amiodarone, azithromycin) may increase exposure to olaparib. Caution should therefore be exercised.

6.2.3.4 Effect of olaparib on other drugs

The efficacy of hormonal contraceptives may be reduced if co-administered with olaparib.

Based on limited *in vitro* data, olaparib may increase the exposure to substrates of CYP3A4, OATP1B1, OCT1, OCT2, OAT3, MATE1, and MATE2K.

Based on limited in vitro data, olaparib may reduce the exposure to substrates of CYP2B6.

Caution should therefore be exercised if substrates of these isoenzymes or transporter proteins are co-administered.

Examples of substrates include (use a frequently-updated resource for comprehensive list):

- CYP3A4 hormonal contraceptive, simvastatin, cisapride, cyclosporine, ergot alkaloids, fentanyl, pimozide, sirolimus, tacrolimus, and quetiapine
- CYP2B6 bupropion, efavirenz
- OATP1B1 bosentan, glibenclamide, repaglinide, statins, and valsartan
- OCT1, MATE1, MATE2K metformin
- OCT2 serum creatinine
- OAT3 furosemide, methotrexate

6.2.4 Anticoagulant Therapy

Patients who are taking warfarin may participate in this trial; however, it is recommended that the international normalized ratio (INR) be monitored carefully at least once per week for the first month, then monthly if the INR is stable. Subcutaneous heparin and low molecular weight heparin are permitted.

6.2.5 Anti-emetics/Anti-diarrheals

If a patient develops nausea, vomiting, and/or diarrhea, then these symptoms should be reported as AEs and appropriate treatment of the event given. An information sheet for patients regarding management and reporting of diarrhea can be found in Appendix C.

6.2.6 Administration of other Anti-Cancer Agents

Patients must not receive any other concurrent anti-cancer therapy, including investigational agents, while on study treatment. Patients may continue the use of bisphosphonates or denosumab for bone disease and corticosteroids for the symptomatic control of brain metastases provided the dose is stable before and during the study and the agents were started at least 4 weeks prior to beginning study treatment.

6.3 **Duration of Therapy**

Treatment will continue until one of the following criteria applies:

- Disease progression per RECIST version 1.1 criteria
- Intercurrent illness that prevents further administration of treatment
- Unacceptable adverse event(s)
- Bone marrow findings consistent with MDS or AML
- Patient decides to withdraw from the study
- General or specific changes in the patient's condition render the patient unacceptable for further treatment in the judgment of the investigator
- Clinical progression
- Patient non-compliance
- Pregnancy
 - All women of child bearing potential should be instructed to contact the investigator immediately if they suspect they might be pregnant (e.g., missed or late menstrual period) at any time during study participation.

- The investigator must immediately notify CTEP in the event of a confirmed pregnancy in a patient participating in the study.
- Termination of the study by sponsor
- The drug manufacturer can no longer provide the study agent

The reason(s) for protocol therapy discontinuation, the reason(s) for study removal, and the corresponding dates must be documented in the case report form (CRF).

6.4 **Duration of Follow Up**

Patients removed from study for adverse events will be followed until resolution or stabilization of the adverse event. Patients will be followed in clinic or by telephone on an approximately every 3 month schedule for 2 years after study participation ends to collect information related to disease status, subsequent anti-cancer therapy and any new diagnosis of AML or MDS. Patients will continue to be followed every 6 months thereafter until death or withdrawal of consent to ascertain any new diagnosis of AML or MDS, and the status of those conditions if diagnosed.

7. DOSE DELAYS AND MODIFICATIONS

7.1 Required Parameters for Initiation of a Treatment Cycle

A new cycle of therapy may begin only if the following criteria are met:

- ANC \geq 1,000/µL
- Hemoglobin ≥ 9 g/dL (for cycle 1, day 1; ≥ 8 g/dL for all other cycles)
- Platelets $\geq 100,000/\mu L$
- Grade ≥ 2 non-hematologic adverse events (except for alopecia) have resolved to grade ≤ 1 , acceptable grade 2 (in the opinion of the treating investigator), or baseline.

7.2 General Principles

The following guidelines apply for dose reductions and delays:

- Dosing for a given cycle will be based on adverse events observed during the prior cycle. When multiple adverse events occur, the modification that would require the patient to receive the lowest dose combination of the study drugs is used.
- When toxicity requires a new treatment cycle to be delayed, both agents should be held until the toxicity resolves and then resumed simultaneously. Deviations from this approach should be discussed with the principal investigator.
- If toxicity requires a study agent to be held during the dosing phase (days 1-7) of a cycle, the other study agent may be continued at the investigator's discretion. If toxicity resolves, treatment with the agent that was held should generally resume at the time of the next scheduled cycle (i.e. the missed doses should not be made up). When an adverse

event results in a study agent being interrupted during a cycle, all planned assessments for that cycle will otherwise occur as scheduled.

- A subject may incur up to 2 dose reductions of each study agent prior to discontinuation of that agent. Furthermore, TMZ may not be dose reduced below 25 mg/m² daily, and olaparib may not be dose reduced below 100 mg BID; in the event reduction below such dose level is indicated, that study agent should be discontinued. However, after discontinuation of one study agent, the other study agent may be continued at the discretion of the treating investigator after an assessment of the overall risk-/benefit ratio for the patient.
- For non-hematologic adverse events that have not resolved at the scheduled start of a cycle per Section 7.1, treatment may be delayed for up to 3 weeks. If, after a 3 week delay, adverse events have still not resolved, in general the patient should be removed from the study. For the management of non-resolving hematologic toxicity, please see Section 7.4.3.

7.3 Dose Levels for Olaparib and Temozolomide

The following dose levels for both agents will be used during this study and apply to the recommended management given throughout this section. If a patient requires more than 2 dose reductions of a study agent, that study agent should be discontinued.

Olaparib dose reductions on study treatment

Initial Olaparib Dose	Dose reduction 1	Dose reduction 2	
200 mg BID	150 mg BID	100 mg BID	

TMZ dose reductions on study treatment	
--	--

Initial TMZ Dose	Dose reduction 1	Dose reduction 2
$75 \text{ mg/m}^2 \text{ QD}$	$50 \text{ mg/m}^2 \text{ QD}$	$25 \text{ mg/m}^2 \text{ QD}$

7.4 Management of Hematologic Toxicity

7.4.1 General Approach

Observed Hematologic Toxicity	Recommended Management
ANC $< 500/\mu$ L and/or	Delay cycle. Monitor complete blood
Platelets $< 50,000/\mu L$	count at least weekly. When criteria for
	new cycle are met, resume at one dose
Grade 3 or 4 neutropenic fever requiring	level lower for the agent to which
oral or intravenous antibiotics	toxicity is assessed.

Grade 3 thrombocytopenia with bleeding		
Hemoglobin $< 7 \text{ g/dL}$		
Other hematologic adverse events \geq grade 3 deemed clinically significant by the treating investigator.		
ANC 500-999/µL and/or	Delay cycle. Monitor complete blood	
Platelets 50,000/mcL - 99,999/mcL and/or	count at least weekly. When criteria for	
Hemoglobin $< 8 \text{ g/dL}$	new cycle are met, resume treatment at	
	same dose level.	

7.4.2 Use of transfusions and colony stimulating factors

The use of blood product transfusions (packed red blood cells and platelets) is permitted per institutional guidelines. Erythropoietin stimulating agents may be used per institutional and National Comprehensive Cancer Network (NCCN) guidelines at the treating investigator's discretion. In the event of cytopenias requiring dose modifications and/or delays, the use of G-CSF as primary prophylaxis in subsequent cycles is permitted per institutional guidelines and investigator judgement, particularly in situations where patients appear to be deriving benefit from the study treatment. The use of thrombopoietin agonists for the management of thrombocytopenia is not recommended.

7.4.3 Management of prolonged hematologic toxicity

Should any subject develop evidence of prolonged hematologic toxicity, including but not limited to ≥ 2 week interruption/delay in study drug administration due to any of the following, additional monitoring is indicated:

- grade 3 anemia (Hgb <8 g/dL)
- grade 3 neutropenia (ANC <1000/mcL)
- grade 3 thrombocytopenia (platelets <50/mcL) and/or
- development of transfusion dependence for red blood cells or platelets

In any of these cases, weekly blood counts including reticulocytes and peripheral smear should be monitored. If toxicity has not resolved to \leq grade 1 within 3 weeks of study drug treatment being held, the patient should be referred to a hematologist for further evaluation and the patient should be removed from the study. Bone marrow biopsy should be considered for evaluation including cytogenetics. Patients who develop MDS or AML while on study treatment should discontinue study participation and be managed appropriately by a hematologist oncologist.

7.4.4 Dose re-escalation of olaparib

Patients who have undergone dose modification of olaparib may be considered for dose reescalation of that drug if they complete 2 cycles of treatment without dose delays and/or modifications (of any study agent). In that situation, the dose of olaparib may only be reescalated by one dose level on one occasion

7.5 Management of Non-Hematologic Toxicities Attributed to Olaparib

Olaparib may be modified for non-hematologic toxicities per below:

Diarrhea Attributed to Olaparib	Management Guidelines
\leq Grade 1	No change in dose.
Grade 2	No change in dose. Evaluate for infectious etiology if clinically indicated. Institute anti-diarrheal therapy. If diarrhea persists at grade 2 or higher for more than 5 days despite supportive care, interrupt olaparib or delay cycle (as appropriate) and manage supportively. Reinstitute at same dose when symptoms improve to \leq grade 1.
	Recurrent grade 2 diarrhea: Interrupt olaparib or delay cycle (as appropriate). Evaluate for infectious etiology. Manage supportively. Upon resolution to \leq grade 1, resume at one dose level lower for olaparib.
Grade 3	Interrupt olaparib or delay cycle (as appropriate) until \leq grade 1. Evaluate for infectious etiology if clinically indicated. Institute anti-diarrheal therapy. Resume at one dose level lower for olaparib when symptoms improve to \leq grade 1.
Grade 4	Discontinue olaparib permanently.

Other Non-Hematologic Toxicity Attributed to Olaparib	Dose Reduction
Grade 1 or 2	No change in dose. Continue therapy at the investigator's discretion.
Grade 3 non-hematologic toxicity deemed clinically significant by the treating investigator and not attributable to TMZ or underlying disease	Interrupt olaparib or delay cycle (as appropriate) until event resolved to grade ≤ 1 , acceptable grade 2 (in the opinion of the treating investigator), or baseline. Resume at one dose level lower for olaparib.
Grade 4 non-hematologic toxicity not attributable to TMZ or underlying disease	Discontinue olaparib permanently.

7.5.1 Renal Impairment

Olaparib has not been studied in patients with severe renal impairment ($CrCl \le 30 \text{ mL/min}$) or end-stage renal disease; if patients develop severe renal impairment ($CrCl \le 30 \text{ mL/min}$) or end stage renal disease, the case should be discussed with the CTEP Medical Monitor. Investigators

should be aware that olaparib may cause artificial increases in the blood creatinine level. These effects are often mild and occur early in treatment.

Non-Hematologic Toxicity Attributed to TMZ	Dose Reduction
Intolerable grade 2 toxicity	Interrupt TMZ or delay cycle (as appropriate) until resolved to grade 1, or deemed tolerable with supportive care.
Grade $3/4$ fatigue, nausea, constipation and/or diarrhea which persist ≥ 3 days despite optimal supportive care	Interrupt TMZ or delay cycle (as appropriate) until event resolved to grade 1, acceptable grade 2 (in the opinion of the treating investigator), or baseline. Resume at one lower dose level for
Other grade 3 adverse event deemed clinically significant by the treating investigator.	TMZ.
Grade 4 (except for grade 4 alopecia, fatigue, nausea and vomiting not maximally managed with supportive care)	Discontinue TMZ permanently.

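### Section 7 gives two conflicting actions for persistent grade 4 diarrhea or constipation on temozolomide, and prints a platelet trigger 1,000-fold too low

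*Combined protocol and SAP*

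**What the plan says.** **TMZ table, Section 7.6.** Two rows matter.

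- The dose-reduction row names grade 3/4 "fatigue, nausea, constipation and/or diarrhea which persist" for at least 3 days despite optimal supportive care. The action is to interrupt or delay, then restart TMZ one level lower.
- The stop row names "Grade 4 (except for grade 4 alopecia, fatigue, nausea and vomiting not maximally managed with supportive care". The action is to end TMZ for good.

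**Neighboring rules.** Section 7.2 has a tie-breaker: "When multiple adverse events occur, the modification that would require the patient to receive the lowest dose combination of the study drugs is used". In Section 7.5, grade 4 diarrhea attributed to olaparib has a single action, "Discontinue olaparib permanently". The same action applies to "Grade 4 non-hematologic toxicity not attributable to TMZ or underlying disease".

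**Platelets, Section 7.4.3.** One trigger for the prolonged-toxicity pathway reads "grade 3 thrombocytopenia (platelets <50/mcL) and/or". Once a trigger is met, "In any of these cases, weekly blood counts including reticulocytes and peripheral smear should be monitored". If the toxicity has not settled to grade 1 or less within 3 weeks of holding treatment, the patient is referred to hematology and leaves the study. Section 7.4.1 sets its platelet limits at below 50,000 and at 50,000 to 99,999.

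**The concern.** These rules tell a site what to do with a patient who has severe toxicity, so each event should lead to one action.

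In the TMZ table, one site could restart TMZ at a lower dose after persistent grade 4 diarrhea while another stops it permanently, and both would be following the text. The overlap also runs in an odd direction. Grade 4 diarrhea that clears in under 3 days meets only the stop row, while the longer and more refractory event also has a route back to treatment.

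The platelet figure opens a work-up that goes beyond Section 7.4.1: reticulocytes and smear, then referral and removal at 3 weeks. Section 7.2 sends unresolved hematologic toxicity to Section 7.4.3. Section 11.1 relies on the Section 7.4.3 definition when it allows cytogenetic sampling. Read literally, a platelet count below 50/mcL would almost never start any of this.

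**Working it through.** **1. Rows met by a persistent grade 4 event attributed to TMZ.** The inputs are the two rows of the Section 7.6 table. Persistent means at least 3 days despite optimal supportive care. I treat optimal and maximal supportive care as the same thing, which is an assumption. The qualifier at the end of the exception can attach to vomiting only, to nausea and vomiting, or to the whole list. Each cell counts the rows met (reduce + stop).

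| Event | Vomiting only | Nausea and vomiting | Whole list |
|---|---|---|---|
| Diarrhea | 1 + 1 = 2 | 1 + 1 = 2 | 1 + 1 = 2 |
| Constipation | 1 + 1 = 2 | 1 + 1 = 2 | 1 + 1 = 2 |
| Nausea | 1 + 0 = 1 | 1 + 1 = 2 | 1 + 1 = 2 |
| Fatigue | 1 + 0 = 1 | 1 + 0 = 1 | 1 + 1 = 2 |
| Vomiting | 0 + 1 = 1 | 0 + 1 = 1 | 0 + 1 = 1 |
| **Event types in two rows** | **2** | **3** | **4** |

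Alopecia and all other grade 4 events never meet two rows. Diarrhea and constipation conflict in every column because the reduce row names them at grade 4 and the exception does not name them at all.

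**2. The same events before supportive care is maximal.** The reduce row is not met. Diarrhea and constipation meet the stop row (1 row each). Fatigue, nausea, vomiting and alopecia are excepted and meet no row on any of the three readings. The only rule left for them is the cycle-start rule in Section 7.1, that "non-hematologic adverse events (except for alopecia) have resolved to grade" 1 or less, an acceptable grade 2, or baseline. That rule does not cover alopecia.

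**3. Does Section 7.2 settle the conflict?** Its condition is that several adverse events occur. Here one event falls in two rows, so the condition is not met. By analogy the rule points toward stopping.

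**4. Platelet trigger.** The printed value is 50/mcL and the Section 7.4.1 limit is 50,000/mcL: 50,000 / 50 = 1,000. A thousands convention does not explain the gap. The same list gives neutrophils in full as below 1000/mcL, which agrees with the 500 to 999 band in Section 7.4.1. Its hemoglobin limit of 8 g/dL also agrees. Only the platelet entry is out of line, and a dropped ',000' is almost certainly the cause.

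**The case against.** **On the platelet figure.** It can fairly be called a typo in a gloss. The trigger is named by its grade, adverse events are graded by CTCAE version 5.0, and the list says it is not exhaustive. Section 7.1 blocks a new cycle below 100,000, and Section 7.4.1 already requires counts at least weekly. All of this stands. A reader might infer from the factor of 1,000 that patients with severe thrombocytopenia went unmonitored. The documents do not support that, because the weekly counts and dose rules with correct limits sit a few lines earlier.

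**On the TMZ table.** The direction of Section 7.2 is clear, and a cautious site would apply it and stop TMZ. On that approach short and long grade 4 diarrhea end alike and the odd ordering disappears. Section 7 also describes its content as guidelines and recommended management, and Section 6.3 separately ends treatment for unacceptable events. This lowers the likelihood of divergent practice. It does not remove the conflict, since the reduce row expressly allows a restart at grade 4.

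**On intent.** A reader might infer from Section 7.5 that permanent discontinuation was always meant for grade 4 diarrhea on TMZ. The documents do not show this. Section 7.5 concerns the other drug, and its rule for other grade 4 events sets aside those attributable to TMZ. Which action applies, and how far the qualifier reaches, are clinical choices for the sponsor.

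**Conclusion.** Both passages are wrong as written, and both are minor.

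The table conflict is certain for two event types. It extends to three or four depending on how an ambiguous clause is read. The platelet value is wrong by a factor of 1,000, with small practical risk.

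The number of patients affected cannot be estimated from the documents and is probably few or none. Section 2.4.2 reports no grade 4 or 5 events in the phase 1 lung cancer study that set this dose and schedule, but gives no patient count from which to put a bound on the rate.

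A reader might infer that inconsistent stopping of TMZ undermines the response result. The documents do not support that. Section 9.5.2 keeps eligible patients in the main response analysis whatever their treatment deviations, and the rule of 5 or more responders in 22 is untouched.

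The conclusion rests on the text as extracted from the PDF. Thousands separators survive in Sections 3.1.7 and 7.4.1, so an extraction loss in Section 7.4.3 alone is unlikely.

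**What to change.** **Section 7.4.3.** Change the platelet trigger to <50,000/mcL.

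**Section 7.6.** Give each persistent grade 4 event one action and state which events the qualifier covers. As a cautious default:

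- Limit the dose-reduction row to grade 3 for diarrhea and constipation, so that grade 4 leads only to permanent TMZ discontinuation. This follows the direction of Section 7.2.
- State the reach of the qualifier. If it covers nausea, or nausea and fatigue, limit the reduce row to grade 3 for those events too; otherwise they stay in two rows.
- Add one line for excepted grade 4 events that meet no row, for example to optimize supportive care and start the next cycle only when Section 7.1 is met.

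The sponsor's clinicians should confirm all three choices.

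Two shorter edits fail on their own. Removing grade 4 from the whole reduce row leaves persistent grade 4 fatigue and nausea in no row if the qualifier covers vomiting only. Adding diarrhea and constipation to the exception leaves them in two rows if the qualifier covers the whole list.

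The cost is a few words, one table line and a clinical sign-off, with no change to design, sample size or analysis. Section 5.7.1.3 indicates that all 22 patients have taken part, so only those still on treatment could benefit. Footnote C of the Section 11 calendar provides for such patients as of February 2023.

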7.6 Management of Non-Hematologic Toxicities Related to Temozolomide

7.7 Management of New or Worsening Pulmonary Symptoms

If new or worsening pulmonary symptoms (*e.g.*, dyspnea) or radiological abnormalities occur in the absence of a clear diagnosis, an interruption in study treatment dosing is recommended and further diagnostic workup (including a high-resolution CT scan) should be performed to exclude pneumonitis.

Following investigation, if no evidence of abnormality is observed on CT imaging and symptoms resolve, then study treatment can be restarted, if deemed appropriate by the investigator. If significant pulmonary abnormalities are identified, these need to be discussed with the CTEP Medical Monitor.

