Studies of olaparib in combination with various chemotherapy agents indicate an increase in bone marrow toxicity (anemia, neutropenia, thrombocytopenia) greater than expected if the agents had been administered alone (Investigator's Brochure, 2018). The effects are generally transient, but treatment delays are common and alternative administration schedules/toxicity management processes have been evaluated within some of these studies. When this type of toxicity has occurred, it has been managed by routine clinical practice including dose delays, dose reductions, intermittent dosing and/or the use of supportive care measures, including granulocyte colony stimulating factor (G-CSF).

The incidence of myelodysplastic syndrome/acute myeloid leukemia (MDS/AML) in patients treated in clinical trials with olaparib monotherapy, including long-term survival follow-up, was <1.5% and the majority of events had a fatal outcome (Investigator's Brochure, 2018). If MDS and/or AML are confirmed while on treatment with olaparib, it is recommended that olaparib should be discontinued and the patient be treated appropriately.

Pneumonitis has been reported in <1.0% patients treated with olaparib monotherapy in clinical studies (Investigator's Brochure, 2018). When olaparib was used in clinical studies in combination with other therapies there have been events with a fatal outcome. If patients present with new or worsening respiratory symptoms such as dyspnea, cough and fever, or an abnormal

chest radiologic finding is observed, olaparib treatment should be interrupted and prompt investigation initiated. If pneumonitis is confirmed, olaparib treatment should be discontinued and the patient treated appropriately.

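### Section 2.2.1.5 says to stop olaparib once pneumonitis is confirmed, but Sections 6.3, 7.5 and 7.7 do not carry that rule, and the generic 7.5 table can be read to allow continuation or resumption

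*Combined protocol and SAP*

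**What the plan says.** Section 2.2.1.5 advises interrupting olaparib and investigating promptly when respiratory symptoms appear or worsen, or when chest imaging is abnormal. It then adds: "If pneumonitis is confirmed, olaparib treatment should be discontinued". No grade is attached. The same paragraph reports pneumonitis in fewer than 1.0% of monotherapy patients and warns: "When olaparib was used in clinical studies in combination with other therapies there have been events with a fatal outcome".

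Section 7.7 applies where pulmonary symptoms or radiological changes have no clear diagnosis. It recommends interruption and a workup that includes high-resolution CT. It has two branches:

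- Clean result: "if no evidence of abnormality is observed on CT imaging and symptoms resolve, then study treatment can be restarted", if the investigator agrees.
- Abnormal result: "If significant pulmonary abnormalities are identified, these need to be discussed with the CTEP Medical Monitor".

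Section 6.3 lists the reasons for ending treatment. One is specific to an olaparib risk: "Bone marrow findings consistent with MDS or AML". Pneumonitis is not named, although the general entries for unacceptable adverse events and for investigator judgment could cover it.

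Section 7.5 has a table for other non-hematologic toxicity attributed to olaparib. For grade 1 or 2 it reads: "No change in dose. Continue therapy at the investigator's discretion". For a clinically significant grade 3 event not due to temozolomide (TMZ) or the disease, olaparib is held until grade 1 or lower, "acceptable grade 2 (in the opinion of the treating investigator), or baseline. Resume at one dose level lower for olaparib". Grade 4 means permanent discontinuation.

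**The concern.** Sites make dosing decisions from Sections 6 and 7, not from the background. A site that confirms pneumonitis finds no instruction there to stop olaparib. If it turns to the 7.5 table, it finds a route to keep or restart the drug at grades 1 to 3. Section 7.1 does not close that route: a new cycle may start once a non-hematologic event is back to grade 1 or lower, acceptable grade 2, or baseline, with no exception for pneumonitis.

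The handling of MDS/AML is a useful comparison. Section 2.2.1.5 gives stop advice for both MDS/AML and pneumonitis. The MDS/AML advice is carried into 6.3 and 7.4.3. The pneumonitis advice, worded at least as firmly, is carried into neither 6.3 nor Section 7, and the protocol gives no reason for the difference.

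What is at stake is patient safety. Pneumonitis is an adverse event of special interest in Section 10.3.4, fatal outcomes are reported with combination use, and this trial gives a combination.

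**Working it through.** The plan states no figure on this point, so the check is mainly a comparison of texts, followed by an upper limit on exposure.

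**Step 1. Where pneumonitis appears.** In the text available it is mentioned in four places: 2.2.1.5 (stop rule), 7.7 (workup to exclude it), 10.1.1 (listed as rare but serious) and 10.3.4 (expedited reporting). Only 2.2.1.5 says what to do with olaparib after confirmation. The patient handouts in Appendices B and C could not be checked.

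**Step 2. Section 7.7 for a confirmed case.** An abnormal CT fails the restart condition, so 7.7 does not authorize a restart. If the abnormality is significant, a discussion follows, but no outcome is prescribed. Two situations are left uncovered: an abnormality judged not significant fits neither branch, and a diagnosis that is clear from the start falls outside the opening condition of 7.7.

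**Step 3. The 7.5 table against 2.2.1.5.**

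| Grade, attributed to olaparib | 7.5 table | Against 2.2.1.5 |
|---|---|---|
| 1-2 | No dose change; continuing is discretionary, so stopping is also open | Allows what 2.2.1.5 advises against |
| 3, clinically significant, not due to TMZ or disease | Hold until resolved as defined, then resume one level lower | Allows resumption, conditional on resolution |
| 4, not due to TMZ or disease | Permanent discontinuation | Agrees |

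**Step 4. Who can be affected.** Section 5.7.1.3 speaks of the 22 patients who participated, and footnote C of the Study Calendar refers to patients remaining on study as of 2/2023. The February 2023 version therefore reaches only those still on treatment. Their number, k, is not given; I assume 1, 5 and 10 to show a range. With p as the risk per patient and patients taken as independent, the expected number of cases is k × p, and the chance of at least one is 1 − (1 − p)^k.

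- p = 1%, the monotherapy ceiling in 2.2.1.5: expected cases 0.01, 0.05, 0.10; chance 1 − 0.99^k = 1.0%, 4.9%, 9.6%.
- p = 3%, the ceiling of the rare-but-serious column in 10.1.1: expected cases 0.03, 0.15, 0.30; chance 1 − 0.97^k = 3.0%, 14.1%, 26.3%.

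Both inputs are ceilings, so all results are upper limits under the assumed k. The 3% value is a general frequency column, looser than the pneumonitis-specific 1%. Neither is a rate for olaparib with TMZ, or for patients already on long-term treatment.

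**The case against.** The strongest reply is that the rule is already in the protocol and only a cross-reference is missing. A reader might infer from the grade 3 row that 7.5 orders the opposite of 2.2.1.5. The documents do not support that:

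- Section 7.5 opens permissively: olaparib may be modified as the tables describe. The table in question is a catch-all, whereas pulmonary events have their own section, and a specific section would ordinarily govern.
- The only restart route in 7.7 requires a CT without abnormality, and significant abnormalities go to the Medical Monitor.
- Resumption under the grade 3 row requires resolution first, and 7.2 says that patients whose non-hematologic events are unresolved after a 3-week delay should in general leave the study.
- Section 10.3.4 requires expedited reporting of every pneumonitis event, whatever its seriousness or cause, so CTEP will know of it.

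It is also fair to say that 6.3 does not enumerate the events of special interest: liver injury and new primary malignancy are not named there either. The absence of pneumonitis from 6.3 alone would prove little.

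These points stand as limits on the size of the problem. They do not remove it. None states what happens to olaparib after confirmation, the protocol does not say that 7.7 overrides 7.5, and the 3-week limit does not reach an event that resolves sooner. Discussion and reporting would still leave 2.2.1.5 and the 7.5 table pointing different ways.

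**Conclusion.** The concern holds as an inconsistency between the background rule and the operative sections. Section 2.2.1.5 says olaparib should be discontinued once pneumonitis is confirmed; 6.3, 7.5 and 7.7 do not repeat this; and the 7.5 table, applied literally, leaves room to continue at grade 1-2 or to resume after a resolved grade 3 event. It should be corrected because the event can be fatal and the repair is small.

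The probability is low. On the 2.2.1.5 ceiling, fewer than 0.01 to 0.10 cases would be expected among an assumed 1 to 10 remaining patients, and harm would further require that the existing safeguards fail to prompt a stop.

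Two wider conclusions that a reader might draw are not supported. The protocol is not without a pneumonitis rule: it has one, in the wrong place for dosing decisions. Nor does anything here bear on the response rate, the sample size or the decision rule.

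**What to change.** 1. In 7.7, add that olaparib is discontinued if pneumonitis is confirmed, consistent with 2.2.1.5.
2. In 6.3, list confirmed pneumonitis as a reason for stopping olaparib.
3. In the 7.5 table for other non-hematologic toxicity, add: except pneumonitis, see 7.7.

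A sentence on TMZ after confirmed pneumonitis would be helpful but is optional, because 7.2 already provides that "after discontinuation of one study agent, the other study agent may be continued at the discretion of the treating investigator".

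The cost is protocol wording only, with no added procedures. The small downside is that patients with low-grade pneumonitis lose the option to continue olaparib.
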